2.8. Medical procedures involved

For the LimFlow procedure, please refer to the product instructions for use (IFU).

3. Justification for the design of the clinical investigation

3.1. Results of the preclinical testing

The LimFlow System has undergone extensive verification and validation testing. This includes device and packaging specific performance specifications, as well as transit, sterility, pre-clinical, biocompatibility and accelerated aging testing. Test samples were manufactured in accordance with a Device Master Record (DMR) using trained operators to nominal specifications and documented within a Design History Record (DHR).

Extensive *in vitro*, *in vivo*, and *ex vivo* studies have been successfully performed with the LimFlow System and verification testing for the catheter has been completed. Testing on the device included comprehensive design verification and validation testing. The following testing was completed on the LimFlow System:

- Biocompatibility testing
- Mechanical testing
- Packaging testing
- Shelf-life testing
- Sterilization validation
- Preclinical animal and cadaver studies

3.2. Clinical data

In the absence of treatment, Peripheral Vascular Disease (PVD) may progress to critical limb ischaemia (CLI), which is characterized by profound chronic pain and extensive tissue loss that restricts revascularization options and frequently leads to amputation. CLI is estimated to have an incidence of approximately 50 to 100 per 100 000 per year and is associated with mortality rates as high as 20% at 6 months after onset.

Interventional radiologists have been aggressively trying to treat CLI by attempting to open up Chronic Total Occlusions (CTOs) or bypassing them in the sub-intimal space using such products as the Medtronic Pioneer catheter which tunnels a wire into the sub-intimal space at the CTO and then attempts to re-enter the vessel after the occlusion. Once a wire is in place, one can place a stent to provide a bypass conduit passed the occlusion. More conventional approaches to treating PVD are also used in CLI treatment once (if) a wire gets across the occlusion. These conventional methods include PTA, stenting, and, more recently, drug eluting balloons and stents.

The LimFlow approach to treating CLI involves the concept of venous arterialization, which has been performed surgically for many years with first clinical surgical cases reported in the early 1900s.¹² Numerous small series of clinical trials have been published using a surgical approach and recent publications summarized this work.^{3,5} In conclusion, venous arterialization was considered as a viable alternative before major amputation is undertaken in “no-option” patients with critical limb ischaemia.

Several clinical studies have been conducted with the LimFlow System in Europe, Singapore, and the United States.⁶ Results from these studies supported the CE-mark approval of the device in October 2016 and on-going investigation in the United States. The results from these studies have been presented at international congresses and published, demonstrating safety and feasibility of percutaneous deep vein arterialization. The most recent publication demonstrates the long-term viability of the therapy by presenting two year follow-up data.⁷

4. Risks and benefits

4.1. Anticipated clinical benefits

The patients designated for percutaneous deep vein arterialization have critical limb ischaemia with no treatment option other than major amputation. These patients have had repeated percutaneous procedures to use angioplasty to open up the below-the-knee vessels, but the re-occlusion rate is high and once the foot is deserted (lack of blood circulation to the foot), ischaemia and necrosis quickly set in. Necrotic tissue has to be cut away to allow healthy tissue a chance to heal. Infection is a major complication that can rapidly become systemic leading to mortality. Critical limb ischaemia patients are desperate as all medical experts have told them that there are no more possible treatments. The lack of options highlights percutaneous deep vein arterialization is a last hope treatment for these patients, who have exhausted all other possibilities. For this reason, the benefits of percutaneous deep vein arterialization with the LimFlow System far outweigh the known risks associated with this device and readily available percutaneous angioplasty equipment.

4.2. Anticipated adverse device effects

The following adverse events are considered to be anticipated when performing any percutaneous catheterization and will be assessed during the course of the study:

- Allergic reaction, including anaphylactic shock and Quincke's oedema
- Vascular complications at access site, including bleeding events and hematoma
- Arterial and venous thromboembolic events, including angina or myocardial infarction, stroke or transient ischaemic event, pulmonary embolism, deep vein thrombosis, and limb ischaemia
- Contrast-induced nephropathy and renal failure
- Local or systemic infection
- Oedema
- Pain

4.3. Residual risks associated with the device

The LimFlow System was reviewed in accordance with a risk management process that complies with the international standard on the application of risk management to medical devices EN ISO 14971:2012. The risk management process entailed an analysis of potential risks and an evaluation of their acceptability in the light of the intended therapeutic use of the system. The purpose of the risk analysis was to identify and characterize undesirable events that could result in harm. For each identified hazard the risks were estimated by factoring in the probability of occurrence and severity of the harm. The design verification report was reviewed to verify that all risk control measures identified as necessary to reduce risk to acceptable levels had been implemented and that no risks would arise from the implementation of control measures. It was concluded that all risks associated with the identified hazards had been reduced to acceptable levels and that the overall risk of the use of the LimFlow System was determined to be acceptable. The LimFlow System received CE-mark in October 2016.

4.4. Risks associated with participation in the clinical investigation

In addition to the risks associated with the device, risks associated with participation in the clinical investigation are limited to the risks associated with the exams required for the clinical investigation. Those have been reduced to minimal levels by complying with standard of care procedures and not requiring any invasive measurement or exam.

4.5. Possible interactions with concomitant medical treatments

Possible interactions with concomitant medical treatments have been reduced by excluding patients with medical conditions necessitating medical treatments that could potentially interfere with the percutaneous deep vein arterialization procedure. Please refer to Section 6.3.2 *"Exclusion criteria"* on page 15.

4.6. Steps that will be taken to control or mitigate the risks

The following steps have or will be taken by LimFlow SA to control or mitigate the risks during the course of this post-market study:

- The use of standard medical grade materials that have been thoroughly characterized and tested to assure biocompatibility.
- Extensive pre-clinical evaluation including in vitro bench testing, animal and cadaver study.
- The well-established, standard nature of the endovascular procedures and techniques to be used.
- The ability to quickly and safely remove the LimFlow System from the procedure; the physician may elect to discontinue the use of the device at any time in favour of alternate devices.
- Frequent follow-up visits are conducted in the first year post-operatively to allow for systematic monitoring and surveillance of the index limb, allowing for early detection of hemodynamically significant stenoses in the graft that may occur in the absence of obvious symptoms.
- Potential subjects will be screened by an independent committee to ensure that all subjects meet defined eligibility criteria.
- Investigators will receive device training and will be proctored for their first case, and then for as many cases as they deem necessary to perform the procedure proficiently.

4.7. Risk-to-benefit rationale

The associated risks proposed in this study are similar to risks posed by other interventional and vascular surgery procedures. The benefit to the subjects enrolled in this study is the potential for improved blood flow to the foot, reducing or eliminating the need for major amputation. The potential benefit of reduced or no amputation of the foot greatly outweighs the standard endovascular/surgical risks associated with this procedure in this “no-option” patient population. It is therefore concluded, from the information currently available, that the risks inherent in the use of the device are in line with the generally accepted state of the art, have been reduced to a level as low as reasonably practicable and are outweighed by the anticipated benefits. The proposed clinical investigation is designed to gather evidence to support this preliminary risk assessment. The subjects to be enrolled in the clinical investigation are thus not expected to be exposed to any undue risks.

5. Objectives and hypotheses of the clinical investigation

5.1. Objectives

The objective of this post-market study is to collect “real-life” clinical data among a population of patients treated with the commercially-available LimFlow System in order to evaluate the **safety and effectiveness** of the LimFlow System in creating a below-the-knee arterio-venous fistula for venous arterialization in subjects with critical limb ischaemia.

5.2. Hypotheses

Results of the LimFlow System risk assessment indicated that device-related risks had been reduced to levels as low as reasonably practicable and comparable with the state of the art. However, although the risks associated with the use of the LimFlow System were comparable with the state-of-the-art, the clinical experience was insufficient to completely characterize the nature and incidence of device-related procedural complications or late clinical complications. Therefore, post-market clinical follow-up was indicated to more precisely assess the nature and incidence of potential risks or to confirm that their prevalence lied below the threshold of concern.

5.3. Claims and intended performance to be verified

The LimFlow System is intended to treat critical limb ischaemia by minimally invasively creating an arterio-venous bypass graft to achieve venous arterialization. The objective of this post-market study is to evaluate the **safety and effectiveness** of the LimFlow System in creating a below-the-knee arterio-venous fistula for venous arterialization in subjects with critical limb ischaemia.

5.4. Risks and anticipated adverse effects to be assessed

The following adverse events are considered to be anticipated when performing any percutaneous catheterization and will be assessed during the course of the study:

- Allergic reaction, including anaphylactic shock and Quincke's oedema
- Vascular complications at access site, including bleeding events and hematoma
- Arterial and venous thromboembolic events, including angina or myocardial infarction, stroke or transient ischaemic event, pulmonary embolism, deep vein thrombosis, and limb ischaemia
- Contrast-induced nephropathy and renal failure
- Local or systemic infection
- Oedema
- Pain

6. Design of the clinical investigation

6.1. General

6.1.1. Type of clinical investigation

This study is a single-arm, open-label, prospective, post-market follow-up study to be conducted on up to 25 eligible patients (roll-in subjects plus 20 analysis subjects) with a twelve-month follow-up period. This study was designed and is to be conducted in compliance with the ISO 14155:2020 standard.

6.1.2. Measures to be taken to minimize or avoid bias

In addition to the screening and enrolment of consecutive patients, an independent committee will act as a medical monitor in order to minimize or avoid bias during the course of the study. The independent committee will consist of at least two (2) physicians with experience in surgical and/or endovascular treatment of critical limb ischaemia patients, who are independent from LimFlow SA and are not investigators in the study. Furthermore, members of the independent committee are neither past or current users of the LimFlow System nor involved with the manufacturer supplying the LimFlow System. Specifically, the independent committee will be responsible for performing the following tasks:

- **Screening:** review of all potential patients for compliance with key eligibility criteria I-2 and I-3
- **Endpoints:** assessment of technical success, patency, and wound healing
- **Adverse events:** two-step process involving (1) independent review of all adverse events by a medical monitor and (2) adjudication of relevant adverse events following a 2 + 1 algorithm

6.1.3. Primary and secondary endpoints

Primary endpoint

- Amputation-free survival

Secondary endpoints

- Complete wound healing
- Primary and secondary patency
- Limb salvage
- Technical and procedural success

6.1.4. Methods and timing for assessing, recording, and analysing variables

Timing for performing visits and assessing variables during the study follow-up period are presented in Table 4 below. Additional post-treatment evaluations performed outside of the follow-up window will be considered “unscheduled”.

Table 4. Time windows

Visit	Target	Interval	Minimum	Maximum
Two (2) weeks	15 days	± 5 days	10 days	20 days
One (1) month	30 days	± 7 days	23 days	37 days
Two (2) months	60 days	± 10 days	50 days	70 days
Three (3) months	90 days	± 14 days	76 days	104 days
Six (6) months	180 days	± 14 days	166 days	194 days
Nine (9) months	270 days	± 14 days	256 days	284 days
Twelve (12) months	360 days	± 28 days	332 days	388 days

All variables will be recorded on electronic Case Report Forms (eCRFs) specifically designed for the study and provided by LimFlow SA to the investigational centres. Collected variables will be analysed using IBM SPSS statistics software, version 17 or later.

6.1.5. Equipment to be used for assessing the clinical investigation variables

Standard evaluation tools such as the Rutherford classification⁸ or the SVS WIF1 (Wound – Ischaemia – foot Infection) classification system⁹ will be used for the overall assessment of critical limb ischaemia at baseline and follow-up visits. Pain will be evaluated using a numerical rating scale and the EuroQol (EQ-5D) questionnaire¹⁰ will be used to assess the patients Quality of Life.

The eKare inSight digital wound management platform (eKare, Inc., Fairfax, Virginia, United States of America) will be used for photographing, scanning, and assessing wounds at screening and follow-up visits. eKare inSight® is an FDA registered Class 1 medical device and is CE marked. Additionally, eKare is ISO 13485 certified and is fully compliant with FDA 21 CFR Part 820, Part 11. One (1) eKare insight platform will be provided by LimFlow to each participating clinical site for the purpose of the study.

6.1.6. Any procedures for the replacement of subjects

Patients who have signed a consent form and have not undergone the procedure will be replaced; however, patients who drop-out during the trial or withdraw their consent after the procedure will not be replaced.

6.2. Device(s) used and comparator(s)

6.2.1. Description of the exposure to the device(s)

Exposure to the medical devices is described in Section 2.8 “*Medical procedures involved*” on page 10 as well as in Section 6.4.3 “*Treatment*” on page 19.

6.2.2. Justification of the choice of comparator(s)

Not applicable as this post-market study is a single-arm study performed in a population of patients with no therapeutic option (other than amputation).

6.2.3. List of any other medical device or medication to be used

Other medical devices or medications to be used are similar to those used when performing a transcatheter, percutaneous intervention in the below-the-knee vasculature. The treatment is to be delivered under general anaesthesia or conscious sedation with regional block, therefore anaesthetic medications will be administered to the patient prior to the intervention. In addition, anticoagulant medication (heparin) will be administered in order to attain and maintain appropriate systemic anticoagulation as verified by ACT or other similar testing. Iodine contrast media will also be injected intravascular to visualize the vasculature under fluoroscopy.

6.2.4. Number of device(s) to be used

The ultrasound system is a reusable device therefore one (1) unit can be used to perform several interventions. The extension cable set, the arterial and venous catheter set, and the valvulotome are single-use devices; at least one (1) unit of each should be used for every patient treated. Several stent grafts may be implanted in every patient depending on the vasculature—typically one (1) stent graft used as a “crossing stent” and at least one (1) stent graft used as an “extension stent”.

6.3. Subjects

6.3.1. Inclusion criteria

- I-1. Subject must be > 21 and < 95 years of age
- I-2. Clinical diagnosis of symptomatic critical limb ischaemia, defined as Rutherford category 5 or 6
- I-3. Assessment that no conventional surgical or endovascular treatment is possible
- I-4. Proximally, the target in-flow artery at the cross-over point must be treatable with a 3.5 – 4.0 mm stent after pre-treatment (by visual estimate), and be <50% stenosed
- I-5. Subject is willing and has adequate support to comply with protocol requirements, including medication regimen and follow-up visits

6.3.2. Exclusion criteria

- E-1. Concomitant hepatic insufficiency, deep venous thrombus in target limb, uncorrected coagulation disorders, or current immunodeficiency disorder
- E-2. Life expectancy less than 12 months
- E-3. Patient currently taking coumarin/warfarin which, in the opinion of the attending physician, interferes with the patient's treatment
- E-4. Any significant medical condition which, in the attending physician's opinion, may interfere with the patient's optimal treatment
- E-5. Patient currently participating in another investigational drug or device study that has not completed the primary endpoint or that clinically interferes with the endpoints of this treatment
- E-6. Patient unable to give consent
- E-7. Pregnant or breastfeeding women
- E-8. Documented myocardial infarction or stroke within previous 90 days
- E-9. Patients suffering from renal insufficiency (GFR value less than 30 ml/min/1.73 m²) who are not on haemodialysis
- E-10. Patients with vasculitis and/or untreated popliteal aneurysms
- E-11. Patients with acute limb ischaemia
- E-12. Prior peripheral arterial bypass procedure above or below the knee which could inhibit proximal inflow to the stent graft
- E-13. Lower extremity venous disease with significant oedema in the target limb that may inhibit the procedure and/or jeopardize wound healing, in the investigator's opinion
- E-14. Known or suspected systemic or severe infection (e.g., WIfI foot Infection grade of 3)
- E-15. Known or suspected allergies or contraindications to stainless steel, nickel, or contrast agent that cannot be adequately pre-treated, or patients who cannot receive anticoagulation or antiplatelet aggregation therapy
- E-16. Severe heart failure, which in the opinion of the investigator may compromise subject's ability to safely undergo a percutaneous procedure (e.g., known ejection fraction of < 40%, NYHA Classification III-IV)

6.3.3. Point of enrolment

Once any component of the LimFlow System is introduced into the body, the subject will be considered to be enrolled in the study and subject to all follow-up requirements. If the device is introduced but implantation is either not attempted or unsuccessful, subjects will be followed through 30 days for safety only, or through resolution or stabilization of any device- or procedure-related adverse events, whichever is longer; those subjects will then be exited from the study and will not be replaced. In addition, "roll-in" subjects performed to avoid a learning curve bias will be included the study but excluded from the endpoint analysis. In some instances, "roll-in" subjects within the study may not be required for any study site who has performed LimFlow System procedures outside the study in the commercial setting.

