2.7. Training and experience needed

The procedure itself should be performed by vascular surgeons and/or interventionalists experienced in interventional techniques such as complex percutaneous transluminal angioplasty and stenting in the lower limb. Study investigators will be selected based on their experience in performing below-the-knee interventions and duly trained by LimFlow SA on the percutaneous deep vein arterialization specific medical procedure. In order to avoid a learning curve bias, each study investigator will be required to first perform at least one (1) successful revascularization in a “roll-in” subject. “Roll-in” subjects will be included the study but excluded from the endpoint analysis. In addition, a LimFlow SA representative will attend the treatments performed in each site in order to assist the physician on technical issues as well as to ensure that treatment characteristics and potential complications are duly recorded.

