6.3.5. Number of subjects and expected duration

The number of subjects required to be included in the clinical investigation was set to up to 25 eligible subjects, which includes any “roll-in” subjects and 20 subjects for analysis. The time needed to select this number (*i.e.*, the enrolment period) was initially estimated to be twelve (12) months, however due to the worldwide pandemic and impact it has had to study enrolment, the study recruitment and enrolment period will be extended. The enrolment period is extended to allow the full cohort of subjects which is anticipated to be by the end of October 2022.

Following enrolment in the clinical investigation, each subject’s participation to this post-market study is expected to last twelve (12) months.

Therefore, this post-market clinical study is expected to last approximately four years, from the actual starting date in December 2019.

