14.5. Emergency contact details

Serious adverse events and serious adverse device effects must be reported to the sponsor LimFlow SA. Contact details are as follows:

LimFlow SA
 [name]
Director of European Clinical Affairs
 E-mail: [contact]
 [contact]

15. Vulnerable population

Not applicable for this post-market study.

16. Suspension or premature termination of the investigation

In the event of unforeseen or increased risks to subjects encountered during the course of the study, LimFlow SA, the Ethics Committee, the Competent Authority, or the Investigator may decide to suspend or terminate the clinical study. Such decision would be made after discussion with all parties.

If the investigator terminates or suspends the study without prior agreement with LimFlow SA, he/she will promptly provide all details to the institution, LimFlow SA, and the Ethics Committee. If the investigation is terminated or suspended by LimFlow SA, the investigator will be promptly informed, who must then inform the Ethics Committee. If the Ethics Committee terminates or suspends the study, the investigator will promptly inform LimFlow SA with written explanation.

Subjects will continue to be followed per the clinical investigational protocol unless it has been determined by the investigator that the continued follow-up may jeopardize the rights, safety, and/or welfare of the subject.

17. Publication policy

The data generated by this clinical study are the property of the sponsor, and should not be disclosed without their prior written permission. These data may be used by the sponsor now and in the future for presentation or publication at sponsor's discretion or for submission to governmental regulatory agencies. The principal investigator may publish or present the study results with prior consent of the sponsor, but will not disclose confidential information. Prior to submission by a principal investigator for publication or presentation, the sponsor will be provided with the opportunity to review the submission for confidential information and accuracy. The possibility of a publication in a peer-reviewed journal will be sought.

18. Definitions

Amputation	Major amputation is defined as amputation of the index limb at the level above the ankle. Minor amputation is defined as amputation(s) of the index limb (including metatarsals) at the level below the ankle.
Amputation-free survival	Defined as the percentage of subjects with limb salvage and survival.

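### Subjects whose implantation fails or is not attempted leave the study after about 30 days, so their month-12 limb and vital status is not assured, and the plan does not say whether they count in amputation-free survival

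*Combined protocol and SAP*

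**What the plan says.** All references are to the combined protocol and SAP.

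- **Enrolment and exit (6.3.3).** A subject is enrolled when any component enters the body. After a failed or unattempted implantation the subject is "followed through 30 days for safety only, or through resolution or stabilization of any device- or procedure-related adverse events, whichever is longer". Once that period is over, participation ends and no new patient is recruited in their place.
- **Stated exclusion (6.3.3, also 2.7).** Roll-in "subjects performed to avoid a learning curve bias will be included the study but excluded from the endpoint analysis". No other group is expressly excluded.
- **Replacement before the procedure (6.1.6).** "Patients who have signed a consent form and have not undergone the procedure will be replaced".
- **Numbers (6.3.5).** Up to 25 subjects, made up of roll-in "subjects and 20 subjects for analysis", each expected to take part for twelve months.
- **Primary endpoint (6.1.3, 18).** AFS: "Defined as the percentage of subjects with limb salvage and survival". The definition gives no denominator, time point or rule for unknown status. Limb salvage, a secondary endpoint, is equally open.
- **Statistics (7.1 to 7.5).** No analysis population is defined and there is no rule for subjects who exit early. Missing data are counted, and withdrawn or lost subjects appear in a patient tree.
- **Adverse events (14.2, 14.4).** All adverse events are recorded. Subjects who have one stay under treatment and medical supervision to 12 months or resolution, whichever is longer.

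**The concern.** A failed-implant subject is enrolled, and so could belong in a percentage of subjects, but is released about eleven months before the end of the planned follow-up. Deaths and major amputations before exit should be captured as adverse events. Later ones need not be.

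The exit is not random. It follows failure of the procedure being evaluated, in patients whom Section 2.2 describes as facing major amputation. If these subjects do worse than implanted subjects, leaving them out or censoring them at exit makes AFS and limb salvage look better than they are. If they do equally well, it does not.

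Because the denominator is not fixed, it could also be chosen after the data are seen, and Section 7.3 allows interim analyses at any time. Section 7.2 states no hypothesis, so what is at stake is a distorted or non-reproducible descriptive estimate. No pass/fail decision is affected.

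**Working it through.** **1. Does any section settle who counts?**

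- *For inclusion:* only roll-ins are expressly excluded. Failures are not replaced, whereas consented patients who never had the procedure are.
- *For exclusion:* the follow-up is for safety only, the roll-in exclusion is worded as an addition to the failed-implant rule, and the objective in 5.1 is "clinical data among a population of patients treated with the commercially-available LimFlow System".
- Section 6.3.4 covers withdrawal, loss to follow-up and exit on reaching the endpoint, but not exit after failed implantation. Sections 7.1 to 7.5 are silent.
- Section 14.4 may keep some subjects under supervision to month 12. It does not reach those without an adverse event, and it asks for no endpoint data.

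The question stays open. On either reading something is missing: the month-12 data if these subjects count, or a statement of exclusion if they do not.

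**2. Is there a figure to reproduce?** No. Section 7.2 says the 20 subjects were not derived statistically, and no event rate or failure rate is given.

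**3. Size without assumed rates.** Take N = 20 non-roll-in enrolled subjects, k failed implants, u of them event-free at exit with unknown later status, and x implanted subjects event-free at day 360.

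- Implanted-only AFS = x/(20 − k)
- All-enrolled AFS lies between x/20 and (x + u)/20
- Undetermined width = u/20: 0, 5 and 10 points for u = 0, 1 and 2

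The values of x below are illustrative. The intervals are exact (Clopper-Pearson).

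| Case | Implanted-only | All enrolled |
|---|---|---|
| k = 1, x = 14, u = 0 (event known before exit) | 14/19 = 73.7% | 14/20 = 70.0% |
| k = 2, x = 13, u = 2 | 13/18 = 72.2% (95% CI 46.5 to 90.3) | 13/20 = 65.0% (40.8 to 84.6) to 15/20 = 75.0% (50.9 to 91.3) |

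The first row shows that the denominator matters even when nothing is unknown: 73.7 − 70.0 = 3.7 points. In the second row the undetermined width is 10 points, against confidence intervals 40 to 44 points wide.

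**4. How likely is a failure?** For an assumed failure rate f, P(at least one in 20) = 1 − (1 − f)^20.

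| f (assumed) | 1% | 3% | 5% | 10% |
|---|---|---|---|---|
| P(at least one) | 18% | 46% | 64% | 88% |

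These are probabilities of any failure. A failure that is event-free at exit and unknown later is less likely.

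**5. Direction and size of bias (illustration).** Assume k = 1, AFS of 70% if implanted and 30% if not.

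- True AFS = (19 × 0.70 + 0.30)/20 = 68.0%
- Failure excluded: 70.0%, a bias of +2.0 points whenever the events occur
- Failure censored at day 30: estimate = [(19·sI + sF)/20] × 0.70/sI, where sI and sF are the event-free proportions at day 30 and sI = 0.70^(1/12) = 0.971

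| Failed-implant events by day 30 | sF | Bias (points) |
|---|---|---|
| Constant hazard, 0.30^(1/12) | 0.905 | +1.76 |
| One quarter | 0.825 | +1.47 |
| Half | 0.65 | +0.84 |
| Three quarters | 0.475 | +0.21 |

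**The case against.** The text can be read as placing failed implants outside the effectiveness analysis, for the reasons listed under exclusion above. After a failed implant, month-12 limb status reflects other care rather than the device, so including these subjects is partly a choice of estimand. Failures are not hidden either: technical success requires stent-graft placement, procedural success builds on it, and a full patient tree would let a reader work out the bounds. If the amputation risk materialises early, most events fall before exit and are recorded. Every rate used above is assumed, the shifts are within sampling error, and by version 4.4 (July 2022) enrolment was expected to end in October 2022.

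Much of this stands, and it limits the size of the point. It does not remove it. The exclusion reading is plausible but nowhere stated, and there is evidence the other way. Technical and procedural success show that failures happened, not what became of those limbs by month 12. A confidence interval does not cover an undefined denominator or outcome-related exit. Early events reduce the censoring bias but not the denominator effect.

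Some early failures may fall among roll-ins, since under Section 2.7 "each study investigator will be required to first perform at least one (1) successful revascularization in a" roll-in subject. But Section 6.3.3 allows that step to be waived at sites with commercial experience, and it is unclear whether a failed first case is a roll-in or an analysis subject.

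**Conclusion.** The concern holds and should be fixed. Followed exactly, Section 6.3.3 leaves month-12 status unassured for a group defined by failure of the procedure, and the plan does not say whether that group counts in AFS or limb salvage.

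The size is modest: 5 points undetermined per failed implant with unknown later status, and 3.7 points between denominators in the one-failure example. This rests on 20 non-roll-in enrolled subjects, on reading the endpoint at month 12, and on at least one failure in that set. An upward bias needs the further assumption that failed-implant subjects fare worse. Confidence is moderate, because the documents give neither a failure rate nor an outcome rate.

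**What to change.** - **Section 6.3.3:** collect vital status and major-amputation status to day 360 for every enrolled subject, including failed or unattempted implants. Use the telephone, letter and general practitioner contacts described in 6.3.4 and 6.4.4. Add no clinic visits.
- **Section 7.1:** state whether failed implants count. The proposal is to report AFS and limb salvage at day 360 for all enrolled non-roll-in subjects, with the implanted-only result alongside.
- **Method, fixed before analysis:** a percentage with exact 95% CI, calculated once with unknown status as event-free and once as an event. The two coincide when status is complete.
- **Subjects already exited:** seek status where consent and ethics approval allow; otherwise report the bounds.
- **Sections 6.3.3 and 14.4:** reconcile the exit rule with the follow-up of subjects who have adverse events.

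**Cost.** One amendment to protocol and consent wording, because those contact routes were written for subjects who cannot be reached rather than for exited ones, and one status check per affected subject. The commitment in Section 13 to no more visits than standard of care is kept. Reported AFS may be lower than an implanted-only figure. Prospective benefit is limited this late and some status may not be recoverable, but the denominator and the bounds can still be fixed before analysis. Section 7.1 foresees pooling with the early feasibility study, so if that study uses the same exit rule, the implanted-only set must also be reported for the pooled analysis.
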